### 7.5.1 Tumor Tissue Specimens

Archival or recently collected FFPE tumor tissue (in the form of paraffin embedded block of a minimum of 10 unstained slides) will be collected if possible prior to enrollment. Available specimens must be sent at screening to Moffitt Cancer Center for retrospective determination of PD-L1 status using an analytically verified IHC assay. A biopsy sample from participants who experience progression at any time while on treatment is optional but strongly encouraged for the purposes of understanding mechanisms of resistance to therapy. Biopsy samples may be used for the assessments listed below. Tumor tissue collection details are provided in Section 7.5.4.

### 7.5.2 Characterization of Tumor Infiltrating Lymphocytes (TILS) and Tumor Antigens

Immunohistochemistry may be used to assess the number and composition of immune infiltrates in order to define the immune cell subsets present within FFPE tumor tissue before and after exposure to therapy. These immunohistochemistry analyses will include, but not necessarily be limited to, the following markers: CD3, CD4, CD8, CD45RO, FOXP3, PD-1, PD-L1 and PD-L2.

### 7.5.3 DNA and RNA Genomic Assessment

DNA or RNA extracted from tumor provided may be participant to whole genome or exome sequencing using next-generation sequencing to identify mutational load and transcriptional expression.

### 7.5.4 Tumor Sample Collection Details

Archival tumor specimens are expected. Pathology report should be provided with tumor samples. For participants without available archival tissue, a new biopsy is not required as long as a pathologic diagnosis of small cell lung cancer has been established. Formalin-fixed paraffin embedded tissue may be evaluated also by fluorescence in situ hybridization (FISH), genetic mutation detection methods, and/or by quantitative polymerase chain reaction (QPCR) for exploratory analyses of prognostic or predictive molecular markers

associated with SCLC (eg, gene mutation, amplification or overexpression), to determine if these factors influence response to ipilimumab and nivolumab. Such analyses will be completed retrospectively and within the scope of informed consent.

If feasible, tumor biopsies or surgical specimens obtained throughout the participant's standard of care treatment course may be obtained. Where appropriate, changes in expression of immunoregulatory proteins may be assessed in these specimens with the consent of the participant.

### **7.5.5 Peripheral Blood Markers**

A variety of factors that may affect the immunomodulatory properties and efficacy of nivolumab will be investigated in peripheral blood specimens taken from all participants prior to or during treatment. Data from these investigations will be evaluated for associations with response, survival, and/or safety (adverse event) data. Several analyses may be completed and are described briefly below.

### **7.5.6 Single Nucleotide Polymorphisms (SNPs)**

Whole blood will be collected from all participants prior to treatment to generate genomic DNA for Single Nucleotide Polymorphism (SNP) analyses and serve as a reference for tumor mutational profiling, unless restricted by local regulations. These analyses will focus on SNPs within genes associated with PD-1 and other immunoregulatory signaling pathways to determine if natural variation within those genes is associated with response to ipilimumab/nivolumab and/or with AEs during treatment.

### **7.5.7 Serum Soluble Factors**

To understand the prevalence of circulating proteins and the impact they may have on the clinical activity of ipilimumab/nivolumab, the protein concentrations of a panel of cytokines, chemokines, and other relevant immunomodulatory, serum-soluble factors (eg, soluble PD-L1) may be investigated at baseline and during treatment.

### **7.5.8 Peripheral Blood Mononuclear Cells**

Peripheral blood mononuclear cells in whole blood taken from participants at baseline and on treatment and will be analyzed by flow cytometry or other methods (e.g., ELIspot) to assess immune cell activity.

### **7.5.9 Peripheral Blood DNA and RNA Genomic Assessment**

DNA or RNA extracted from peripheral blood samples collected throughout the study may be participant to whole genome or exome sequencing using next-generation sequencing to identify mutational load and transcriptional expression.

## 8 ADVERSE EVENTS

NCI CTCAE Version 4.0 will be utilized for identification and grading of all adverse events.

An Adverse Event (AE) is defined as any new untoward medical occurrence or worsening of a preexisting medical condition in a clinical investigation participant administered study drug and that does not necessarily have a causal relationship with this treatment. An AE can therefore be any unfavorable and unintended sign (such as an abnormal laboratory finding), symptom, or disease temporally associated with the use of study drug, whether or not considered related to the study drug. The causal relationship to study drug is determined by a physician and should be used to assess all adverse events. The causal relationship can be one of the following:

- Unrelated: The Adverse Event is *clearly not related* to the investigational agent(s)
- Unlikely: The Adverse Event is *doubtfully related* to the investigational agent(s)
- Possible: The Adverse Event *may be related* to the investigational agent(s)
- Probable: The Adverse Event is *likely related* to the investigational agent(s)
- Definite: The Adverse Event is *clearly related* to the investigational agent(s)

Adverse events can be spontaneously reported or elicited during open-ended questioning, examination, or evaluation of a participant. (In order to prevent reporting bias, participants should not be questioned regarding the specific occurrence of one or more AEs.)

The study sponsor, Moffitt Cancer Center, will be reporting adverse events to regulatory authorities and ethics committees according to local applicable laws including FDA Code of Federal Regulations 21 CFR Parts 312 and 320. In addition, K08 CA231454-01A1 Grant support will be provided through Moffitt Cancer Center.

### 8.1 Serious Adverse Events

A Serious Adverse Event (SAE) is any untoward medical occurrence that at any dose:

- Results in death
- Is life-threatening (defined as an event in which the participant was at risk of death at the time of the event; it does not refer to an event which hypothetically might have caused death if it were more severe)
- Requires in-patient hospitalization or causes prolongation of existing hospitalization (see **NOTE** below)
- Results in persistent or significant disability/incapacity
- Is a congenital anomaly/birth defect
- Is an important medical event (defined as a medical event(s) that may not be immediately life-threatening or result in death or hospitalization but, based upon appropriate medical and scientific judgment, may jeopardize the participant or may require intervention [eg, medical, surgical] to prevent one of the other serious outcomes listed in the definition above.) Examples of such events include, but

are not limited to, intensive treatment in an emergency room or at home for allergic bronchospasm; blood dyscrasias, or convulsions that do not result in hospitalization.

- Potential drug-induced liver injury (DILI) is also considered an important medical event. (See Section 8.6 for the definition of potential DILI.)
- Suspected transmission of an infectious agent (eg, pathogenic or nonpathogenic) via study drug is an SAE.
- Although pregnancy, overdose, cancer, and potential drug-induced liver injury (DILI) are not always serious by regulatory definition, these events must be handled as SAEs. (See Section 8.4 for reporting pregnancies.)
- Any component of a study endpoint that is considered related to study therapy (eg, death is an endpoint, if death occurred due to anaphylaxis, anaphylaxis must be reported) should be reported as SAE (see Section 8.1.1 for reporting details).

NOTE:

The following hospitalizations are not considered SAEs:

- a visit to the emergency room or other hospital department < 24 hours that does not result in admission (unless considered an important medical or life-threatening event)
- elective surgery, planned prior to signing consent
- admissions as per protocol for a planned medical/surgical procedure
- routine health assessment requiring admission for baseline/trending of health status (eg, routine colonoscopy)
- medical/surgical admission other than to remedy ill health and planned prior to entry into the study. Appropriate documentation is required in these cases
- admission encountered for another life circumstance that carries no bearing on health status and requires no medical/surgical intervention (eg, lack of housing, economic inadequacy, caregiver respite, family circumstances, administrative reason).

### **8.1.1 Serious Adverse Event Collection and Reporting**

The Investigator Brochure (IB) contains Reference Safety Information to determine expectedness of serious adverse events for expedited reporting. Following the participant's written consent to participate in the study, all SAEs, whether related or not related to the study, must be collected, including those thought to be associated with protocol-specified procedures.

All SAEs must be collected that occur during the screening period and within 100 days of discontinuation of dosing. If applicable, SAEs must be collected that relate to any later protocol-specified procedure. The investigator must report any SAE that occurs after these time periods and that is believed to be related to the

study or protocol-specified procedure. An SAE report must be completed for any event where doubt exists regarding its seriousness. All SAEs must be reported to BMS Worldwide Safety. The BMS SAE form should be used to report SAEs.

If the investigator believes that an SAE is not related to the study, but is potentially related to the conditions of the study (such as withdrawal of previous therapy or a complication of a study procedure), the relationship must be specified in the narrative section of the SAE Report Form.

SAEs, whether related or not related to study drug, and pregnancies must be reported to BMS (as below) and to the study sponsor, Moffitt Cancer Center, through the MCRN coordinating center within 24 hours of awareness of the event. SAEs must be recorded on the SAE Report Form; pregnancies on a Pregnancy Surveillance Form (electronic or paper forms).

To ensure patient safety, each serious adverse event must be reported to the BMS, the PI and to the MCRN coordinating center within 24 hours of the investigational staff's knowledge. All participating sites will report SAEs by completing an SAE report in OnCore, the electronic data capture system. The SAE must be reported by email ([[contact]](mailto:[contact])) to the MCRN within 24 hours of discovery.

The preferred method for SAE data reporting collection is through the eCRF. The paper SAE/pregnancy surveillance forms are only intended as a back-up option when the eCRF system is not functioning. In this case, the paper forms are to be transmitted via email or confirmed facsimile (fax) transmission to both :

**SAE Email Addresses:** [[contact]](mailto:[contact]) , [[contact]](mailto:[contact])

**SAE Facsimile Numbers:** MCRN [contact], BMS [contact]

**SAE Telephone Contacts:** [contact]

If only limited information is initially available, follow-up reports are required. (Note: Follow-up SAE reports should include the same investigator term(s) initially reported.)

If an ongoing SAE changes in its intensity or relationship to study drug or if new information becomes available, the SAE report must be updated and submitted within 24 hours to Sponsor or designee using the same procedure used for transmitting the initial SAE report.

All SAEs must be followed to resolution or stabilization.

The Sponsor/Investigator will ensure that all SAEs in the clinical database are reported to BMS and any applicable health authority during the conduct of the study. This reconciliation will occur at least quarterly and be initiated by the sponsor/investigator. Sponsor/investigator will request a reconciliation report from: [[contact]](mailto:[contact]). During reconciliation, any events found to not be reported previously to BMS must be sent to [[contact]](mailto:[contact]).

A Suspected Unexpected Serious Adverse Reaction (SUSAR) is a subset of SAEs and will be reported to the appropriate regulatory authorities and investigators following local and global guidelines and requirements.

## 8.2 Nonserious Adverse Events

A *nonserious adverse event* is an AE not classified as serious.

### 8.2.1 Nonserious Adverse Event Collection and Reporting

NCI CTCAE Version 4.0 will be utilized for grading of all nonserious adverse events.

The collection of nonserious AE information should begin at initiation of the study. Data will be captured in OnCore, Moffitt's Clinical Trials Database. To obtain access to OnCore, the site research staff must complete forms provided by the MCRN Regulatory Coordinator. Once the completed forms are received, the site coordinator will receive DUO access, logon/password, and information on how to access OnCore. The MCRN Coordinating Center will provide OnCore training to the site once initial access is granted and on an ongoing basis, as needed.

Nonserious AEs should be followed to resolution or stabilization, or reported as SAEs if they become serious (see Section 8.1.1). Follow-up is also required for nonserious AEs that cause interruption or discontinuation of study drug and for those present at the end of study treatment as appropriate. All identified nonserious AEs must be recorded and described on the nonserious AE page of the OnCore CRF. All nonserious AEs (not only those deemed to be treatment-related) should be collected continuously during the treatment period and for a minimum of 100 days following the last dose of study treatment. Completion of supplemental CRFs may be requested for AEs and/or laboratory abnormalities that are reported/identified during the course of the study.

## 8.3 Laboratory Test Result Abnormalities

The following laboratory test result abnormalities should be captured on the nonserious AE CRF page or SAE Report Form (paper or electronic using OnCore) as appropriate:

- Any laboratory test result that is clinically significant or meets the definition of an SAE
- Any laboratory test result abnormality that required the participant to have study drug discontinued or interrupted
- Any laboratory test result abnormality that required the participant to receive specific corrective therapy

It is expected that wherever possible, the clinical rather than laboratory term would be used by the reporting investigator (eg, anemia versus low hemoglobin value).

## 8.4 Pregnancy

If, following initiation of the study, it is subsequently discovered that a study participant is pregnant or may have been pregnant at the time of study exposure, including during at least 6 half lives after product

administration, the investigator must immediately notify the BMS Worldwide Safety and the Principal Investigator/designee of this event and complete and forward a Pregnancy Surveillance Form within 24 hours of awareness of the event and in accordance with SAE reporting procedures described in Section 8.1.1. An SAE must also be entered into the OnCore system and an email sent to the MCRN ([[contact]](mailto:[contact])) and to BMS ([[contact]](mailto:[contact])) within 24 hours of discovery.

In most cases, the study drugs will be permanently discontinued in an appropriate manner (eg, dose tapering if necessary for participant safety). Please call the Principal Investigator within 24 hours of awareness of the pregnancy.

In the rare event that the benefit continuing the study drug is thought to outweigh the risk, after consultation with the study sponsor, the pregnant participant may continue study drug after a thorough discussion of benefits and risk with the participant.

Protocol-required procedures for study discontinuation and follow-up must be performed on the participant unless contraindicated by pregnancy (eg, x-ray studies). Other appropriate pregnancy follow-up procedures must be performed on the participant.

Follow-up information regarding the course of the pregnancy, including perinatal and neonatal outcome and, where applicable, offspring information must be reported on the Pregnancy Surveillance Form.

Any pregnancy that occurs in a female partner of a male study participant should be reported to BMS and the MCRN Coordinating Center. In order for the study to collect any pregnancy surveillance information from the female partner, the female partner must sign an informed consent form for disclosure of this information. Information on this pregnancy will be collected on the Pregnancy Surveillance Form.

## **8.5 Overdose**

An overdose is defined as the accidental or intentional administration of any dose of a product that is considered both excessive and medically important. All occurrences of overdose must be reported as an SAE (see Section 8.1.1 for reporting details).

## **8.6 Potential Drug-Induced Liver Injury (DILI)**

Wherever possible, timely confirmation of initial liver-related laboratory abnormalities should occur prior to the reporting of a potential DILI event. All occurrences of potential DILIs, meeting the defined criteria, must be reported as SAEs (see Section 8.1.1 for reporting details).

Potential drug induced liver injury is defined as:

1. AT (ALT or AST) elevation > 3 times upper limit of normal (ULN)

AND

2. Total bilirubin > 2 times ULN, without initial findings of cholestasis (elevated serum alkaline phosphatase),

AND

3. No other immediately apparent possible causes of AT elevation and hyperbilirubinemia, including, but not limited to, viral hepatitis, pre-existing chronic or acute liver disease, or the administration of other drug(s) known to be hepatotoxic.

## **8.7 Other Safety Considerations**

Any significant worsening noted during interim or final physical examinations, electrocardiogram, x-ray filming, any other potential safety assessment required or not required by protocol should also be recorded as a nonserious or serious AE, as appropriate, and reported accordingly.

## **8.8 Protocol Monitoring Committee**

A Protocol Monitoring Committee (PMC) will be established to provide oversight of safety and efficacy considerations in the protocol. The PMC meets monthly and reviews accrual, patterns and frequencies of all adverse events, protocol violations and when applicable, internal audit results.

# **9 STATISTICAL CONSIDERATIONS**

## **9.1 Lead in Safety Observation**

We will utilize 6-9 patient safety lead in as described in the Section 4.1 with a dose-limiting toxicity period of 13 weeks. We will initially enroll 6 patients. If 0 or 1 of 6 patients develops unacceptable toxicity, then we will proceed with the study as outlined below (to accrue an additional 46 patients). If 2 patients develop unacceptable toxicity, we will enroll an additional 3 patients to determine the rate of unacceptable toxicity with 9 patients. If 3 or more patients develop unacceptable toxicity during any portion of the safety lead in phase, we will discontinue the study.

Additionally, we will be continually assessing toxicity throughout the study and if at any time 3 of the first 9 patients or greater than 33% of patients experience unacceptable toxicity within the 13 week safety observation period, we will discontinue the study. Following the 13-week safety observation period, toxicity will be assessed on an ongoing basis for all patients prior to each dose of ipilimumab/nivolumab or nivolumab alone until study completion.

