### 4.1 Safety Lead in Design

All patients for the entire study will be treated on the same schedule outlined in Section 4.2. We will utilize a 6 to 9 patient safety lead in endpoint as described in the Section 9.1 with a safety observation period of 13 weeks after initiation of thoracic radiation therapy. We will initially enroll 6 patients and wait until completion of the 13-week safety observation period following initiation of ipilimumab + nivolumab combination treatment. No additional patients will be enrolled until the safety lead in phase is complete.

If 0 or 1 of 6 patients develops unacceptable toxicity:

then we will proceed with the study as outlined below (to accrue an additional 44 patients).

If 2 patients develop unacceptable toxicity:

then we will enroll an additional 3 patients to determine the rate of unacceptable toxicity with 9 patients.

[figure not shown]
If 3 or more patients develop unacceptable toxicity during any portion of the safety lead in phase,

then we will discontinue the study.

Additionally, we will be continually assessing toxicity throughout the study and if at any time 3 of the first 9 patients or greater than 33% of patients experience unacceptable toxicity within the 13-week safety observation period, we will discontinue the study. After the 13-week safety observation period, toxicity will be assessed on an ongoing basis for all patients prior to each dose of ipilimumab/nivolumab or nivolumab alone until study completion. If unacceptable toxicity occurs outside the 13 week safety observation period, that patient will discontinue treatment on the study according to discontinuation criteria (Section 6.5.3.4). The protocol monitoring committee will evaluate all patients who discontinue the study due to unacceptable toxicity on a monthly basis. If the monitoring committee feels that the study regimen is unsafe, we will discontinue the study.

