#### **6.5.3.4 Discontinuation Criteria**

Treatment with study therapy should be permanently discontinued for the following:

- Any Grade 2 drug-related uveitis or eye pain or blurred vision that does not respond to topical therapy and does not improve to Grade 1 severity within the re-treatment period OR requires systemic treatment
- Any Grade 3 non-skin, drug-related AE lasting > 7 days, with the following exceptions:
  - Grade 3 drug-related uveitis, pneumonitis, bronchospasm, neurologic toxicity, hypersensitivity reaction, or infusion reaction of any duration requires discontinuation
  - Grade 3 drug-related laboratory abnormalities do not require treatment discontinuation except:
    - ◆ Grade 3 drug-related thrombocytopenia > 7 days or associated with bleeding requires discontinuation
    - ◆ Any drug-related liver function test (LFT) abnormality that meets the following criteria require discontinuation:
      - AST or ALT > 8 x ULN
      - Total bilirubin > 5 x ULN
      - Concurrent AST or ALT > 3 x ULN and total bilirubin > 2 x ULN
- Any Grade 4 drug-related AE or laboratory abnormality, except for the following events which do not require discontinuation:
  - Grade 4 neutropenia  $\leq$  7 days
  - Grade 4 lymphopenia or leukopenia
  - Isolated Grade 4 electrolyte imbalances/abnormalities that are not associated with clinical sequelae and are corrected with supplementation/appropriate management within 72 hours of their onset
  - Grade 4 amylase or lipase abnormalities that are not associated with symptoms or clinical manifestations, or radiographic signs of pancreatitis. It is recommended to consult with the Principal Investigator for Grade 4 amylase or lipase abnormalities
  - For Grade 4 endocrinopathy AEs such as adrenal insufficiency, ACTH deficiency, hyper or hypothyroidosis, or glucose intolerance, which resolve or are adequately controlled with physiologic hormone replacement (steroids, thyroid hormones) or glucose controlling agents, respectively, retreatment can be considered after discussion with the Principal Investigator
- Any dosing interruption lasting > 6 weeks from the last dose with the following exceptions:

- Dosing interruptions to allow for prolonged steroid tapers to manage drug-related AEs are allowed. Prior to re-initiating treatment in a participant with a dosing interruption lasting > 6 weeks from the last dose, the Principal Investigator must be consulted

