## 9.2 Phase I/II Sample Size Determination

We propose a single arm, non-randomized phase I/II study, with the goal to evaluate efficacy compared to historical controls. Slotman et al. [5] reported a 6-month progression-free survival (PFS) of 24% with platinum-based chemotherapy and thoracic radiation therapy. We would propose to pursue a phase III randomized controlled study if there is a 20% improvement in 6-month PFS with the addition of combined immune checkpoint blockade as part of the proposed clinical study. Therefore, this regimen would be considered not worthwhile to pursue if the true 6-month PFS is 24% or less and worth pursuing if the true 6-month PFS is 44% or greater. The trial will use a Simon's 2-stage design[49] with 1-sided 0.05 level type I error and 90% power. The total target sample size is 52 patients. During the 1st stage, 18 patients will be accrued. If 4 or fewer patients have not progressed at 6 months, the study will be closed for futility. However, if at least 5 patients have not progressed at 6 months, then the study will continue to accrue an additional 34 patients. Once the total number of patients has accrued (n=52), then the null hypothesis will be rejected if at least 18 patients have not progressed at 6 months. In order to accommodate censoring, we may increase the total sample size by up to 10% (n=57).

- The final PFS analysis is targeted to occur 6 months after the last participant is enrolled
- The final OS analysis is targeted to occur 1 year after the last participant is enrolled.

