## 9.4 Endpoints

### 9.4.1 Primary Endpoints

**Part I: Safety Run In Phase I:** Unacceptable toxicity status at the end of 13-week safety observation period with unacceptable toxicity defined as:

- Any grade 4 immune related adverse event (irAE),
- Any  $\geq$  grade 3 noninfectious pneumonitis,
- 
- Any grade 3 irAE, excluding pneumonitis, that does not downgrade to grade 2 within 7 days after onset of the event despite optimal medical management including systemic corticosteroids or does not downgrade to  $\leq$  grade 1 or baseline within 14 days,
- Liver transaminase elevation  $> 8 \times$  ULN or total bilirubin  $> 5 \times$  ULN,
- Any  $\geq$  grade 3 non-irAE, except for the following exclusions:
  - grade 3 fatigue lasting  $\leq$  7 days
  - grade 3 endocrine disorder (thyroid, pituitary, and/or adrenal insufficiency) that is managed with or without systemic corticosteroid therapy and/or hormone replacement therapy and the participant is asymptomatic
  - grade 3 infusion-related reaction (first occurrence and in the absence of steroid prophylaxis) that resolves within 6 hours with appropriate clinical management
  - grade 3 or 4 neutropenia that is not associated with fever or systemic infection that improves by at least 1 grade within 3 days.

**Part II: Phase II:** The primary endpoint is 6-month PFS status. PFS is defined as the duration from date of registration to date of first documentation of progression assessed by local investigator or symptomatic deterioration (as defined above) or death due to any cause. Patients last known to be alive without report of progression are censored at date of last disease assessment. For patients with a missing scan (or consecutive missing scans) whose subsequent scan determines progression, the expected date of the first missing scan (as defined by the disease assessment schedule) will be used as the date of progression.

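### The 33% toxicity limb has no minimum number of patients, so as written it contradicts the lead-in rule at 2 of 6; separately, the immune-event criterion names grade 4 only

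*Combined protocol and SAP*

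**What the plan says.** Section 9.1 gives two toxicity rules, and 4.1 gives the same two.

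- **Lead-in rule.** Six patients are enrolled first. "If 0 or 1 of 6 patients develops unacceptable toxicity, then we will proceed with the study as outlined below". "If 2 patients develop unacceptable toxicity, we will enroll an additional 3 patients to determine the rate of unacceptable toxicity with 9 patients". Three or more events at any point in the lead-in close the study.
- **Continuous rule.** The study is also discontinued "if at any time 3 of the first 9 patients or greater than 33% of patients experience unacceptable toxicity" within the 13-week safety observation period. Neither section says from which patient the percentage applies, or which patients form its denominator.

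Section 4.1 adds that enrolment pauses until the lead-in is complete, that a committee reviews toxicity discontinuations monthly, and that "If the monitoring committee feels that the study regimen is unsafe, we will discontinue the study".

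The event being counted is defined in 9.4.1. One criterion is "Any grade 4 immune related adverse event (irAE". The pneumonitis criterion carries a greater-than-or-equal sign before "grade 3 noninfectious pneumonitis", and the criterion for events that are not immune-related also starts at grade 3 or higher. The other immune-event criterion covers grade 3 events that do not improve in time. There is also a liver limit.

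**The concern.** The continuous rule is introduced as an addition to the lead-in rule and applies at any time. Nothing confines it to later patients. Both rules therefore cover patients 1 to 6, and at some counts they give opposite instructions. These counts decide whether the trial proceeds, expands or closes, and unacceptable toxicity is also the primary endpoint of Part I. A decision threshold should give one answer for each count.

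The smaller matter is completeness. The immune-event criteria name grade 3 (if slow to improve) and grade 4, but not grade 5. A fatal immune event other than pneumonitis that was recorded only as grade 5, and lay outside the liver limit, would meet no grade-based criterion. In a six-patient lead-in one uncounted event matters: it turns 3 of 6 (stop) into 2 of 6 (add 3 patients), or 2 of 6 into 1 of 6 (proceed).

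**Working it through.** **Inputs.** The two rules come from 4.1 and 9.1. The target of 52 patients, with up to 57 allowed for censoring, comes from 9.2. The documents give no true toxicity rate, so I assume p = 10, 15, 20, 25 and 30%. Section 1.1.3 reports 11% discontinuation for treatment-related events and 30% grade 3-4 drug-related events for this drug regimen without radiation. I treat patients as independent, with status known in order of entry.

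**The plan's own figures.** The toxicity rule has no stated operating characteristics to reproduce. The efficacy design does reproduce (exact type I error 0.0494, power 0.9035) and is not affected by this point.

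**Step 1: smallest count that triggers the percentage limb.**

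| Patients observed | More than 33% | More than one third |
|---|---|---|
| 1-2 | 1 | 1 |
| 3 | 1 | 2 |
| 4-5 | 2 | 2 |
| 6 | 2 | 3 |
| 7-8 | 3 | 3 |
| 9 | 3 | 4 |

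**Step 2: compare with the lead-in rule.**

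- At 2 of 6, 2/6 = 33.3% exceeds 33%: discontinue. The lead-in rule says enrol 3 more.
- With 1 event in patients 1-3, even 1/3 = 33.3% exceeds 33%: discontinue. The lead-in rule proceeds if that is the only event in 6.
- Reading 33% as one third removes the clash at 2/6 and 1/3. It leaves 1/1, 1/2, 2/4 and 2/5, if the rule is checked that early.

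**Step 3: how often these counts arise.** Exactly 2 of 6 has probability 15p²(1−p)⁴. At p = 0.10 this is 15 × 0.01 × 0.6561 = 0.098. Exactly 1 of 6 with the event in patients 1-3 has probability 3p(1−p)⁵. At p = 0.10 this is 3 × 0.10 × 0.59049 = 0.177.

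| p | 10% | 15% | 20% | 25% | 30% |
|---|---|---|---|---|---|
| Exactly 2 of 6 | 10% | 18% | 25% | 30% | 32% |
| 1 of 6, event in patients 1-3 | 18% | 20% | 20% | 18% | 15% |

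**Step 4: chance of stopping by patient 52.** Let q(n, x) be the probability of x events in n patients with no stop so far. Then q(n, x) = (1−p)·q(n−1, x) + p·q(n−1, x−1). Any x that meets the rule at n is removed and added to the stopping probability. The 3-of-first-9 limb is always active.

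| Percentage limb | 10% | 15% | 20% | 25% | 30% |
|---|---|---|---|---|---|
| More than 33%, from patient 1 | 30.0 | 45.0 | 59.9 | 74.2 | 86.3 |
| More than 33%, from patient 6 | 13.0 | 27.1 | 44.5 | 63.3 | 80.1 |
| More than 33%, from patient 10 | 6.1 | 17.4 | 34.7 | 55.6 | 75.5 |
| More than one third, from patient 6 | 5.7 | 16.0 | 31.8 | 51.8 | 72.1 |
| More than one third, from patient 10 | 5.7 | 16.0 | 31.8 | 51.8 | 72.1 |

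Gaps against starting at patient 10, in points:

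- More than 33%, from patient 1: 24, 28, 25, 19 and 11.
- More than 33%, from patient 6: 7, 10, 10, 8 and 5. The whole gap comes from lead-ins with exactly 2 of 6.
- More than one third, from patient 6: zero, because Step 1 never asks for fewer than 3 events at n = 6 to 9, where 3 already stops the study.

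**Step 5: the threshold after patient 9.** More than 33% gives the same counts as one third or more at every n up to 57. It differs from more than one third at n = 12, 15, ... 57, which is 16 of the 48 values from 10 to 57. From Step 4, with the limb starting at patient 10, the largest difference in stopping is 55.6 − 51.8 = 3.8 points.

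**Step 6: the grade 5 gap.** Fatal pneumonitis, fatal events judged not immune-related, liver events beyond the limits, and events recorded at grade 4 before death are all counted. What remains is a fatal immune event, other than pneumonitis, that was never recorded at grade 4 or as prolonged grade 3. I have no rate for this. The one treatment-related death that 1.1.3 describes for this regimen (n = 61) was reported as grade 4 and would count.

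**The case against.** **Context points to the intended order.** The continuous rule follows an explicit 6-to-9-patient algorithm and its first limb concerns the first 9. Read literally, the percentage limb would make 3 of the first 9 redundant, since 3 of 7, 8 or 9 already exceeds 33%. A team is unlikely to close a trial at 1 of 1. I accept this as the likely intent. It remains an inference, because the sentence applies at any time and states no starting point.

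**The size depends on the reading.** Section 4.1 says to enrol 6 patients and wait out the observation period, so a check after each of patients 1-5 is not the obvious practice. A reader might infer from the literal rule that the trial is 24-28 points more likely to stop at true rates of 10-20%. The documents do not support that as the expected effect: it needs checks during patients 1-5 and 33% taken literally. First checked at patient 6, the gap is about 5-10 points, or zero if 33% means one third.

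**The grade 5 gap is narrow and may be an extraction artefact.** In the text read from the PDF, an empty bullet follows the pneumonitis criterion, so lost text cannot be ruled out. Every death is a serious adverse event reported within 24 hours (8.1, 8.1.1), and the committee reviews all adverse events monthly (8.8). A reader might infer that the plan ignores treatment-related deaths. It does not. These backstops make the correction minor, but they do not put the event into the count.

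**Conclusion.** The percentage limb and the lead-in rule conflict as written. The clearest case is 2 of 6, where one sentence closes the study and another adds 3 patients. At assumed true rates of 10 to 30% that count arises in 10 to 32% of lead-ins. The added chance of stopping by patient 52, against a limb that starts at patient 10, is 11-28 points, about 5-10 points or zero, depending on when the limb is first checked and what 33% means. This is a contradiction in a stated threshold and worth correcting, although the likely intent is clear. The figures assume independent patients, status known in entry order, and true rates that the documents do not supply.

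The grade 5 wording is a separate, low-cost correction for a rare event, subject to a look at the original PDF.

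A reader might also infer that clarifying the limb leaves its strictness unchanged. That holds only if 33% was meant literally. If more than one third was meant, counts based on more than 33% are stricter at the 16 patient numbers in Step 5.

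**What to change.** 1. In 4.1 and 9.1, state that the lead-in rule and the 3-of-first-9 limb govern patients 1-9, and that the percentage limb applies from patient 10.
2. Have the investigators choose the threshold, and print the matching stopping counts up to 57 patients:
   - more than 33% (the same as one third or more): 4 at 10-12, 5 at 13-15, 6 at 16-18, then one more every 3 patients to 17 at 49-51, 18 at 52-54 and 19 at 55-57;
   - more than one third: 4 at 10-11, 5 at 12-14, 6 at 15-17, then one more every 3 patients to 18 at 51-53, 19 at 54-56 and 20 at 57.
3. Say which patients the table's n counts, for example those who have completed the 13-week period or had an unacceptable toxicity within it.
4. In 9.4.1, extend the grade 4 immune-event criterion to grade 4 or higher, after checking the empty bullet against the original PDF.

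The cost is wording in three sections and one short table. Sample size, visits and data collection do not change.
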